Week 84	589	548 – 631
Week 96	673	632 – 715
Week 108	757	716 – 799
Week 120	841	800 – 925
Week 144	1009	926 – 1093
Week 168	1177	1094 – 1261
Week 192	1345	1262 – 1429
Week 216	1513	1430 – 1597
Week 240	1681	1598 – 1765
Week 264	1849	1766 – 1933
Week 288	2017	1934 – 2101
Week 312	2185	2102 – 2269
Week 336	2353	2270 – 2437
Week 360	2521	2438 – 2605
Week 384	2689	2606 – 2773
Week 408	2857	2774 – 2941

Table 3. Time Window for Analysis of IMPACT III

Assigned Visit	Nominal Day	Time Window (Rx Day Range)
Week 0	1	≤ 1
Week 12	85	2 – 127
Week 24	169	128 – 253
Week 48	337	254 – 421
Week 72	505	422 – 631
Week 108	757	632 – 799
Week 120	841	800 – 925
Week 144	1009	926 – 1093
Week 168	1177	1094 – 1261
Week 192	1345	1262 – 1429
Week 216	1513	1430 – 1597
Week 240	1681	1598 – 1765
Week 264	1849	1766 – 1933
Week 288	2017	1934 – 2101
Week 312	2185	2102 – 2269
Week 336	2353	2270 – 2437
Week 360	2521	2438 – 2605
Week 384	2689	2606 – 2773
Week 408	2857	2774 – 2941

Table 4. Time Window for Analysis of hs-CRP

Assigned Visit	Nominal Day	Time Window (Rx Day Range)
Week 0	1	≤ 1
Week 24	169	2 – 253
Week 48	337	254 – 421
Week 72	505	422 – 631
Week 108	757	632 – 883
Week 144	1009	884 – 1177
Week 192	1345	1178 – 1429
Week 216	1513	1430 – 1681
Week 264	1849	1682 – 1933
Week 288	2017	1934 – 2101
Week 312	2185	2102 – 2269
Week 336	2353	2270 – 2437
Week 360	2521	2438 – 2605
Week 384	2689	2606 – 2773
Week 408	2857	2774 – 2941

The time window for treatment-emergent adverse events is from the day of the first injection of Study M06-807 study drug to the last non-missing injection date + 70 days.

Definition of Missing Data Imputation

Baseline Value is Missing: Subjects will be excluded from analysis of change and percent change from baseline if baseline evaluation (Baseline of Study M06-806) is missing.

Missing Efficacy and Outcome Evaluations: The following imputation methods will be used to impute missing values in the efficacy analyses. In addition, an observed case analysis will be performed.

When an endpoint in the study is analyzed as observed (this is denoted as Observed Case [OC]), no imputation of the missing values will be performed.

In the subgroup analysis of efficacy variables, Last Observation Carried Forward (LOCF) analysis will also be carried out as sensitivity analysis. The following rules will be used for the LOCF approach:

1. Baseline (the Week 52 visit of Study M06-806) and pre-baseline values will not be used to impute the missing post-baseline values.

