2. Missing values after Study Day 1 will be imputed using the latest non-missing values after Day 1 and prior to the missing value.

Rule for PCDAI and CDAI Calculation

Diary entries will be evaluated for the CDAI calculation for each visit. For each CDAI subscore, the available scores from the most recent diary days (at least 4 days, up to 7 days) prior to actual day of the study visit will be summed, and then multiplied by the corresponding multiplier to get subtotal score. If available diary entries are fewer than 7 days, the subtotal score will be calculated as (summed total available score/number of days) \times 7 \times corresponding multiplier. The three subscores (number of liquid/very soft stools, abdominal pain rating, and general well-being) will then be rounded to one decimal. The final CDAI is rounded to a whole number.

If a subject has fewer than 4 days of diary data, the total CDAI score will not be calculated and will be considered missing.

If a subject has any subscore missing, the corresponding total PCDAI or CDAI score will be missing.

Partial Study Dates: If the day and/or month are missing, the following conventions will be used to impute the missing visit (or assessment) dates other than the dosing dates:

- 01 for missing start day,
- End of month for missing end day,
- January 1st will be used for a missing start month,

- December 31st for missing end month.

In case of partially missing AE start and stop dates, the dates will be imputed by comparing to first dose date of study medication so that the corresponding AEs will be made treatment-emergent whenever possible. If the start date of an AE is partially missing and the month is the same as the start date of a new therapy, the AE will be made treatment-emergent to the new therapy.

In case of missing or partially missing study drug dosing dates, the dates will not be imputed. Subjects will be treated as not receiving dose on that date.

Rounding

Rounding will be performed only for presentation of results. No rounding will be performed before or during analyses/calculations. The ROUND function of SAS will be used to round results for presentation.

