9.0 Study Drug Exposure and Compliance

Study drug exposure (defined below) and the number of injections will be summarized for the ITT population. The number of subjects who dose escalated from eow to weekly administration of study drug will be summarized by visit with frequencies and percentages.

Study drug exposure: Exposure to study treatment in days (d) during Study M06-807 will be defined as follows:

Treatment exposure [d] = the date of last ADA injection in Study M06-807 – date of first ADA injection in Study M06-807 + 14 days.

Treatment Compliance (%), defined as the number of injections received divided by the number of injections planned or expected (in accordance with the study design), during the subject's participation in Study M06-807 and multiplied by 100 (rounded to 0.1%). Treatment Compliance will also be summarized using descriptive statistics.

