10.2 Analysis of Adverse Events

Adverse events will be coded using version 19.1 of the Medical Dictionary for Regulatory Activities (MedDRA). Adverse event data will be summarized and presented using primary MedDRA system organ classes (SOCs) and preferred terms (PTs). The system organ classes will be presented in alphabetical order and the preferred terms will be presented in alphabetical order within each system organ class. The following two types of tables are planned:

1. Crude incidence rate, i.e., the number and percent of subjects with treatment-emergent AEs will be tabulated.
2. Events per 100 patient years of observation: The number of AEs per 100 patient-years of observation will be tabulated.

Treatment-emergent adverse events are defined as new events that begin either on or after the first dose of the study medication in Study M06-806 and within 70 days after the last dose of the study medication in Study M06-807. The treatment-emergent adverse events listed below are of special interest:

- Any adverse event (AE),
- Any serious AE,
- Any AE leading to discontinuation,
- Any severe event,
- Any at least possibly drug-related AE,
- Any at least possibly drug-related serious AE,
- Any AE leading to death,
- Any infection,
- Any serious infection,
- Any legionella infection,
- Any diverticulitis,
- Any opportunistic infection excluding oral candidiasis and TB,
- Any oral candidiasis,
- Any tuberculosis,
- Any active tuberculosis,
- Any latent tuberculosis,
- Any parasitic infection,
- Any reactivation of hepatitis,
- Any progressive multifocal leukoencephalopathy (PML),
- Any malignancy,
- Any lymphoma,
- Any hepatosplenic T-cell lymphoma (HSTCL),
- Any non-melanoma skin cancers (NMSC),
- Any melanoma,
- Any leukaemia,

- Any malignancy other than lymphoma, HSTCL, leukaemia, NMSC or melanoma,
- Any allergic reaction including angioedema/anaphylaxis,
- Any lupus-like reactions and systemic lupus erythematosus,
- Any vasculitis,
- Any cutaneous vasculitis,
- Any non-cutaneous vasculitis,
- Any sarcoidosis,
- Any autoimmune hepatitis,
- Any myocardial infarction,
- Any cerebrovascular accident,
- Any CHF,
- Any pulmonary embolism,
- Any interstitial lung disease,
- Any intestinal perforation,
- Any intestinal stricture,
- Any pancreatitis,
- Any Stevens-Johnson Syndrome,
- Any erythema multiforme,
- Any worsening/new onset of psoriasis,
- Any demyelinating disorder,
- Any amyotrophic lateral sclerosis,

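### An injection with an incomplete date counts as not given, which lowers compliance and, if it is the last injection, ends exposure and the adverse-event window early

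*SAP*

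**What the plan says.** Four places in the SAP bear on this point.

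- **Section 6.0, partial dates.** Other visit and assessment dates have an imputation convention. Dosing dates are excluded from it: "In case of missing or partially missing study drug dosing dates, the dates will not be imputed". The next sentence states the consequence: "Subjects will be treated as not receiving dose on that date".
- **Section 6.0, adverse-event window.** The window runs "from the day of the first injection of Study M06-807 study drug" "to the last non-missing injection date + 70 days".
- **Section 9.0.** Exposure is the last injection date minus the first, plus 14 days. Compliance is "defined as the number of injections received divided by the number of injections planned or expected", times 100. The number of injections is also summarised.
- **Section 10.2.** Treatment-emergent events are those that "begin either on or after the first dose of the study medication in Study M06-806" and fall no later than 70 days after the last dose in Study M06-807. Events beyond 70 days leave the summaries but remain in the data listings.

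**The concern.** A gap in the record of when a dose was given is not evidence that the dose was not given. The rule treats it as such, and the result feeds three outputs.

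Compliance and the number of injections lose every such dose. Exposure loses time if the first or last injection is affected. The adverse-event window is anchored to the last usable date rather than to the last dose, so it can close sooner than the 70 days after last dose that Section 10.2 intends.

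Long-term safety is a study objective (Section 4.1), and adverse events are a primary safety parameter (Section 10.1). At the end of the window the rule can only remove events from the treatment-emergent summaries; it can never add any.

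**Working it through.** The SAP gives no figure on this point, so there is nothing to reproduce. The check is date arithmetic on the SAP's own rules.

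**Inputs.** The dosing interval g is 14 days (eow) or 7 days (ew), from Section 4.2. The tail is 70 days (Section 6.0). The exposure credit after the last injection is 14 days (Section 9.0). Maximum duration is 408 weeks (Section 4.2). Dispensing is mostly 12 weeks apart up to Week 120 and 24 weeks apart from then on (Table 1). The number k of undated injections is an assumption, because the SAP does not give it.

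**Compliance.** The loss is 100 × k / planned injections. For k = 1:

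- 408 weeks eow: 408 / 2 = 204 planned; 100 / 204 = 0.5 points.
- 408 weeks ew: 100 / 408 = 0.2 points.
- 48 weeks eow: 48 / 2 = 24 planned; 100 / 24 = 4.2 points.
- 48 weeks ew: 100 / 48 = 2.1 points.

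A whole undated 24-week dispensing interval holds 12 eow injections. The first such interval ends at Week 144, when 144 / 2 = 72 are planned, so the loss is at most 12 / 72 = 16.7 points. At Week 408 it is 12 / 204 = 5.9 points. Before Week 120 a 12-week interval holds only 6 eow injections.

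**End of window and exposure.** Put the last dated injection at day 0, followed by k undated injections. The true last injection is at day k × g, and the window closes at day 70. Exposure and window are each short by k × g days. Days on drug outside the window are max(0, k × g + c − 70), where c is the credit after the last injection: 14 days as in Section 9.0, or the dosing interval.

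| k trailing | eow: days short | eow: on-drug days outside | ew: days short | ew: outside, c = 14 | ew: outside, c = 7 |
|---|---|---|---|---|---|
| 1 | 14 | 0 | 7 | 0 | 0 |
| 4 | 56 | 0 | 28 | 0 | 0 |
| 5 | 70 | 14 | 35 | 0 | 0 |
| 6 | 84 | 28 | 42 | 0 | 0 |
| 9 | 126 | 70 | 63 | 7 | 0 |
| 10 | 140 | 84 | 70 | 14 | 7 |
| 12 | 168 | 112 | 84 | 28 | 21 |

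The first on-drug day is lost at k = 5 eow, and at k = 9 or 10 ew depending on c. The true last injection itself falls outside only at k = 6 eow (84 > 70) or k = 11 ew (77 > 70). If every eow dose in a final 24-week interval were undated (k = 12), 168 + 14 − 70 = 112 on-drug days would be outside.

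**Undated doses between dated ones.** Exposure and window are unchanged. Only compliance and the injection count fall.

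**Start of window.** Under Section 6.0, one undated first injection moves the start later by one dosing interval, with no buffer. Under Section 10.2 it does not, because that definition starts in Study M06-806. The two definitions need to be reconciled in any case.

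**The case against.** The best defence is that not imputing dosing dates is an explicit, pre-stated convention in a descriptive, single-group study without tests, and that the 70-day tail absorbs most of the effect. Much of this stands. One to four undated trailing eow doses put no on-drug day outside the window, and events that fall out of the summaries stay in the listings. It does not answer the compliance loss, which occurs for every such dose, or the shortened tail, which occurs from the first undated trailing dose. The rule might also be read narrowly, as denying a dose only on one particular date. With the date unknown there is no particular date to apply that to, so in programming the dose would simply drop out.

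A reader might infer more than the SAP supports:

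- **That adverse events on drug are routinely lost.** This needs an unbroken run of at least 5 undated eow doses (9 or 10 ew) at the end of treatment. Nothing in the SAP shows that such runs occur.
- **That exposure is understated in general.** Section 9.0 uses only the first and last injection dates, so doses in between do not matter.
- **That the rule contradicts the convention for partial adverse-event dates** ("the corresponding AEs will be made treatment-emergent whenever possible"). That convention compares with the first dose date and says nothing about the last dose. The two lean in different directions but can both be applied.
- **That event rates are biased downward.** The SAP does not define how patient-years of observation are computed. If they follow the shortened exposure, the denominator shrinks too, and the direction is not fixed.

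**Conclusion.** The point holds in a limited form. The stated rule converts an unknown date into a missed dose. The effect on compliance is certain in direction and small per dose: 0.5 points over 408 weeks eow, 4.2 points over 48 weeks eow. When the last injection is the incomplete one, exposure and the treatment-emergent window are short by 14 days per trailing eow dose or 7 days per trailing ew dose, and the window no longer delivers the 70 days after last dose of Section 10.2.

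These sizes assume that the injections were in fact given and taken on schedule. How often dates are incomplete is unknown, so the total effect cannot be stated. It is probably small unless most of a late dispensing interval is undated. Correction is still worthwhile, because the rule gives a wrong result wherever it applies and is cheap to change.

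**What to change.** Replace the dosing-date rule in Section 6.0 with the following:

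- An injection recorded as given with an incomplete date counts as received, for compliance and for the number of injections.
- For the end of the treatment-emergent window, an incomplete last-injection date is set to the latest date consistent with the recorded part, not before the last dated injection and not after the termination visit.
- An incomplete first M06-807 injection date is set to the earliest consistent date, not before the Week 52 visit of Study M06-806.
- Exposure is reported twice: with these dates, and by fully dated injections only.

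The cost is a few sentences of SAP text and minor programming. There are two downsides. A few events slightly beyond 70 days may enter the summaries. Exposure may be slightly overstated, usually by less than a month when only the day is missing; if patient-years are taken from exposure, this could dilute event rates a little. The second exposure figure shows how much the imputed dates matter.

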7.1 Demographic and Baseline Characteristics

All demographic variables and baseline characteristics will be summarized descriptively based on baseline values from double-blind Study M06-806. Categorical data will be described by frequency and percentage, whereas continuous data will be presented by mean, standard deviation, minimum, 1st quartile, median, 3rd quartile and maximum, and the number of non-missing values. The following demographic variables and baseline characteristics will be summarized for the ITT population.

- Sex [Male, Female],
- Race [White, Black, American Indian/Alaska Native, Native Hawaiian or Other Pacific Islander, Asian, Other],
- Race categories [White, Non-white],
- Ethnicity [Hispanic, Non-Hispanic],
- Age [years],
- Age categories [< 13 years, ≥ 13 years],
- Body weight [kg],
- Body weight categories [< 40 kg, ≥ 40 kg],
- Height [cm],
- BMI [kg/m^2],
- Location of Crohn's disease [Anal/Perianal, Rectum, Gastroduodenum, Colon, Jejunum, Ileum, Other],
- Tobacco/nicotine use at Baseline [User, Ex-user, Non-user, unknown],
- Alcohol use at Baseline [Drinker, Ex-drinker, Non-drinker, unknown],
- Prior infliximab use [No, Yes],
- Initial response to infliximab [No, Yes],
- Loss of response to infliximab [No, Yes],
- Demonstrated a reaction to infliximab [No, Yes],

- Reaction to infliximab [Acute, Delayed],
- Draining cutaneous fistula counts,
- Erythrocyte sedimentation rate (ESR),
- C-reactive protein (CRP) [mg/dL],
- CRP categories [< 1.0 , ≥ 1.0 mg/dL],
- Immunosuppressant use at Baseline [No, Yes],
- Corticosteroid use at Baseline [No, Yes],
- Baseline PCDAI,
- Baseline CDAI (for subjects ≥ 13 years of age),
- Baseline IMPACT III (for subjects greater or equal to 10 years old at Baseline),
- Baseline WPAI.

7.2 Medical History

Medical history data will be summarized and presented using body systems and conditions/diagnoses. The body systems will be presented in alphabetical order and the conditions/diagnoses will be presented in alphabetical order within each body system. The number and percentage of subjects with a particular condition/diagnosis will be summarized. Subjects reporting more than one condition/diagnosis within a body system will be counted only once for that body system.

7.3 Previous Treatment and Concomitant Medications

Previous medications and concomitant medications will be coded by WHO DRUG dictionary. The number and percentage of subjects who had taken medications will be summarized by generic drug name for the ITT population. Previous medications taken prior to the first dose of the previous Study M06-806 will be summarized. Concomitant medications taken during Study M06-807 will be summarized.

Concomitant immunomodulator use at Study M06-806 baseline is defined as the use of immunomodulators [6-mercaptopurine (6-MP), azathioprine (AZA), and methotrexate

(MTX)] if the medication start date was before or equal to adalimumab first dose date and the medication end date was after or equal to adalimumab first dose date. The study required that subjects stayed on concomitant immunomodulators at least through Week 26 in Study M06-806 if they were using those immunomodulators at Study M06-806 baseline. After Week 8, decreases in the dose or discontinuation of Crohn's related concomitant treatments were allowed according to the investigators' medical judgment. Subjects who were in flare or who flared after they had reduced or completely tapered their dose of corticosteroid could have their corticosteroid dose increased or restarted at the discretion of the investigator.

8.0 Patient Disposition

Number of subjects included in each analysis population/analysis set will be summarized. The number and percentage of subjects contributed by each investigator will be summarized for ITT population. Number of subjects who needed a dose increase because of increased weight will be summarized for ITT population. Number of subjects who dose escalated from eow to ew dosing because of flare and number of subjects who dose de-escalated will be summarized as well. The number and percentage of subjects prematurely discontinuing study drug for each reason will be summarized. Subjects may have multiple reasons for prematurely discontinuing study drug, but will be counted only once for the primary reason.

9.0 Study Drug Exposure and Compliance

Study drug exposure (defined below) and the number of injections will be summarized for the ITT population. The number of subjects who dose escalated from eow to weekly administration of study drug will be summarized by visit with frequencies and percentages.

Study drug exposure: Exposure to study treatment in days (d) during Study M06-807 will be defined as follows:

Treatment exposure [d] = the date of last ADA injection in Study M06-807 – date of first ADA injection in Study M06-807 + 14 days.

Treatment Compliance (%), defined as the number of injections received divided by the number of injections planned or expected (in accordance with the study design), during the subject's participation in Study M06-807 and multiplied by 100 (rounded to 0.1%). Treatment Compliance will also be summarized using descriptive statistics.

10.0 Safety Analysis

10.1 General Considerations

Safety analysis will be performed on Safety Analysis Set as defined in Section 5.1.

Adverse events, laboratory data and vital signs are the primary safety parameters, and these will be assessed throughout the study. Safety data will be summarized using descriptive statistics. No statistical tests will be performed.

10.2 Analysis of Adverse Events

Adverse events will be coded using version 19.1 of the Medical Dictionary for Regulatory Activities (MedDRA). Adverse event data will be summarized and presented using primary MedDRA system organ classes (SOCs) and preferred terms (PTs). The system organ classes will be presented in alphabetical order and the preferred terms will be presented in alphabetical order within each system organ class. The following two types of tables are planned:

1. Crude incidence rate, i.e., the number and percent of subjects with treatment-emergent AEs will be tabulated.
2. Events per 100 patient years of observation: The number of AEs per 100 patient-years of observation will be tabulated.

Treatment-emergent adverse events are defined as new events that begin either on or after the first dose of the study medication in Study M06-806 and within 70 days after the last dose of the study medication in Study M06-807. The treatment-emergent adverse events listed below are of special interest:

- Any adverse event (AE),
- Any serious AE,
- Any AE leading to discontinuation,
- Any severe event,
- Any at least possibly drug-related AE,
- Any at least possibly drug-related serious AE,
- Any AE leading to death,
- Any infection,
- Any serious infection,
- Any legionella infection,
- Any diverticulitis,
- Any opportunistic infection excluding oral candidiasis and TB,
- Any oral candidiasis,
- Any tuberculosis,
- Any active tuberculosis,
- Any latent tuberculosis,
- Any parasitic infection,
- Any reactivation of hepatitis,
- Any progressive multifocal leukoencephalopathy (PML),
- Any malignancy,
- Any lymphoma,
- Any hepatosplenic T-cell lymphoma (HSTCL),
- Any non-melanoma skin cancers (NMSC),
- Any melanoma,
- Any leukaemia,

- Any malignancy other than lymphoma, HSTCL, leukaemia, NMSC or melanoma,
- Any allergic reaction including angioedema/anaphylaxis,
- Any lupus-like reactions and systemic lupus erythematosus,
- Any vasculitis,
- Any cutaneous vasculitis,
- Any non-cutaneous vasculitis,
- Any sarcoidosis,
- Any autoimmune hepatitis,
- Any myocardial infarction,
- Any cerebrovascular accident,
- Any CHF,
- Any pulmonary embolism,
- Any interstitial lung disease,
- Any intestinal perforation,
- Any intestinal stricture,
- Any pancreatitis,
- Any Stevens-Johnson Syndrome,
- Any erythema multiforme,
- Any worsening/new onset of psoriasis,
- Any demyelinating disorder,
- Any amyotrophic lateral sclerosis,
- Any reversible posterior leukoencephalopathy syndrome (RPLS),
- Any hematologic disorders including pancytopenia,
- Any liver failure and other liver event,
- Any adalimumab administration related medication error,
- Any injection site reaction.

Adverse events that are reported more than 70 days after last study injection will be excluded from the summaries; however, all reported adverse events will be included in the adverse event data listings.

Adverse events with missing or unknown severity will be categorized as severe. Adverse events with missing or unknown relationship to study drug will be categorized as at least possibly drug-related. A subject who reports more than one adverse event in different system organ classes will be counted only once in the overall total. A subject who reports two or more different preferred terms which are in the same SOC will be counted only once in the SOC total. A subject who reports more than one adverse event with the same preferred term will be counted only once for that preferred term using the most extreme incident (i.e., most "severe" for the severity tables and most "related" for the relationship tables). An overview of planned adverse event tables is provided below.

Treatment-emergent adverse events will be summarized as follows:

- Grouped by System Organ Class and Preferred Term.
- Grouped by System Organ Class, Preferred Term and Severity.
- Grouped by System Organ Class, Preferred Term and Relation to Study Drug.
- Grouped by System Organ Class and Preferred Term with subject numbers.

Treatment-emergent serious adverse events will be summarized as follows:

- Grouped by System Organ Class and Preferred Term.
- Grouped by System Organ Class, Preferred Term and Relation to Study Drug.
- A by-subject listing will be provided.

Treatment-emergent adverse events leading to death or premature discontinuation of study drug will be summarized separately as follows:

- Grouped by System Organ Class and Preferred Term
- A by-subject listing will be provided.

Treatment-emergent adverse events of special interest (listed above) will be summarized as follows:

- Grouped by System Organ Class and Preferred Term.
- A by-subject listing will be provided.

Treatment-emergent AEs (TEAEs) will be listed if less than five subjects had AE data in the dose de-escalation set. Otherwise, the number and percentage of subjects with TEAEs and TEAEs per 100 patient-years will be summarized for the dose de-escalation set. The collection periods for the dose de-escalation set are defined as any event with onset on or after the first dose of ADA treatment in Study M06-806 and up to 70 days after the last study drug injection.

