5.0 Analysis Populations

5.1 Definition of Analysis Populations

The following two study populations will be used for analyses in this study.

Intent-To-Treat (ITT) Population: The ITT population consists of all subjects who received at least one dose of adalimumab in Study M06-807 and also had at least one non-missing efficacy measurement during the study. The ITT population will be used for efficacy analyses in this study.

Safety Population: The safety population consists of all subjects who received at least one dose of adalimumab in Study M06-807. The safety population will be used for safety analyses in this study.

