10.5 Safety Subgroup Analysis

Concomitant immunomodulator use at Study M06-806 baseline defined in Section 7.3 and concomitant corticosteroid use will be used in subgroup analysis for incidence of treatment-emergent serious infections. The incidence of treatment-emergent serious infections and rates of serious infections per patient years for subjects who received adalimumab monotherapy compared with subjects who received adalimumab plus immunomodulators will be summarized. In addition to the analysis of serious infections, the two subgroups (adalimumab monotherapy and adalimumab plus immunomodulators) are further stratified by concomitant corticosteroid use.

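### The SAP starts the treatment-emergent AE window at two different dates about a year apart, and never defines the patient-years used for AE rates

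*SAP*

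**What the plan says.** The SAP fixes the start of the treatment-emergent period in three places.

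- **Section 6.0**, after the visit-window tables: "The time window for treatment-emergent adverse events is from the day of the first injection of Study M06-807 study drug". The window ends 70 days after the last recorded injection.
- **Section 10.2**, general definition: "Treatment-emergent adverse events are defined as new events that begin either on or after the first dose of the study medication in Study M06-806". The end is 70 days after the last M06-807 dose, the same as in Section 6.0.
- **Section 10.2**, dose de-escalation set: "any event with onset on or after the first dose of ADA treatment in Study M06-806", again ending 70 days after the last injection.

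For partly missing AE dates, Section 6.0 says that "the dates will be imputed by comparing to first dose date of study medication", so that the event counts as treatment-emergent where possible. It does not name the study.

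On rates, Section 10.2 says: "The number of AEs per 100 patient-years of observation will be tabulated". The dose de-escalation set also gets events per 100 patient-years, and Section 10.5 asks for "rates of serious infections per patient years". None of these gives a start, an end or a formula for the person-time. The only person-time formula in the SAP is treatment exposure in Section 9.0: the last M06-807 injection date minus the "date of first ADA injection in Study M06-807 + 14 days". It is summarised for the ITT population. The AE analyses use the safety population of Section 5.1: "The safety population consists of all subjects who received at least one dose of adalimumab in Study M06-807".

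**The concern.** Sections 6.0 and 10.2 define the same term, neither is limited to particular tables, and the summary of changes in Section 12 does not mention the difference. An event that began and ended during M06-806 is treatment-emergent under Section 10.2 and is not under Section 6.0. This affects the number and percentage of subjects as well as the event counts, in every AE category: serious events, events of special interest, and the serious-infection subgroups of Section 10.5.

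The patient-years gap compounds this. A programmer looking for a denominator finds only the Section 9.0 exposure formula. It covers M06-807 alone and stops 14 days after the last injection, whereas both AE windows run to 70 days. It would match neither window.

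Long-term safety is part of the study objective (Section 4.1), and these tables are the main evidence on it.

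**Working it through.** The SAP gives no AE rate or count to reproduce. The check compares the sections and then sizes the difference.

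**The definitions side by side**

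| | Start | End |
|---|---|---|
| Section 6.0 | First M06-807 injection | Last injection + 70 days |
| Section 10.2, general | First M06-806 dose | Last M06-807 dose + 70 days |
| Section 10.2, dose de-escalation set | First adalimumab dose in M06-806 | Last injection + 70 days |
| Section 9.0 exposure | First M06-807 injection | Last M06-807 injection + 14 days |
| Patient-years (10.2, 10.5) | Not stated | Not stated |

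**Inputs**

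- Parent study length: 52 weeks (Section 3.1), taken as 364 days from first M06-806 dose to first M06-807 dose.
- Maximum M06-807 duration: 408 weeks (Section 4.2).
- Subjects enrolled: 100 (Section 4.3).
- *L* = days from first to last M06-807 injection. Actual follow-up is not given, so 52, 104, 208 and 408 weeks are assumed: 364, 728, 1456 and 2856 days.
- Assumption: a constant event rate, and the same *L* for every subject.

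**Formulas**

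- Section 6.0 window = *L* + 71 days (70 days plus the day of the first injection).
- Section 10.2 window = 364 + *L* + 71 days.
- Section 9.0 exposure = *L* + 14 days.

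| Weeks, first to last injection | 6.0 window (days) | 10.2 window (days) | 9.0 exposure (days) | Event counts, 10.2 / 6.0 | 10.2 window / exposure | 6.0 window / exposure |
|---|---|---|---|---|---|---|
| 52 | 435 | 799 | 378 | 1.84 | 2.11 | 1.15 |
| 104 | 799 | 1163 | 742 | 1.46 | 1.57 | 1.08 |
| 208 | 1527 | 1891 | 1470 | 1.24 | 1.29 | 1.04 |
| 408 | 2927 | 3291 | 2870 | 1.12 | 1.15 | 1.02 |

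For example, at 52 weeks: 799 / 435 = 1.84, 799 / 378 = 2.11 and 435 / 378 = 1.15.

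The last two columns are the factors by which a constant rate is overstated *if* Section 9.0 exposure serves as the denominator. If patient-years run over the same window as the events, the factor is 1.00 for either start.

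For 100 subjects, the earlier start adds 100 × 364 / 365.25 = 99.7 patient-years of event time.

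**Crude incidence.** For an event with an assumed hazard of 0.10 per year, the percentage of subjects affected is 1 − exp(−0.10 × days / 365.25).

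- 52 weeks: 11.2% (435 days, Section 6.0) versus 19.6% (799 days, Section 10.2).
- 208 weeks: 34.2% (1527 days) versus 40.4% (1891 days).

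A correct denominator for the rates would leave these percentages unchanged, because they depend only on the start date.

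**The case against.** The other side accepts the conflicting start dates but argues that less follows from them.

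- **The M06-806 start may be deliberate.** The dose de-escalation paragraph repeats it, and the SAP anchors baseline, response, demographics and the immunomodulator subgroups to M06-806. This shows that such a window is a legitimate choice. It does not settle which one governs, because the safety population, Rx days and exposure are all anchored to M06-807, and Section 6.0 remains in force.
- **The denominator is named as observation time, not exposure.** Section 9.0 is nowhere linked to AE rates, and a natural reading takes observation to be the AE window itself, which gives a factor of 1.00. This is fair. The overstatement factors are therefore conditional, and the missing definition alone would be a matter of detail. It still needs stating, because with two windows in the text even the natural reading has two answers.
- **The figures are illustrations.** Events may be less completely captured in the 70-day tail, so the factors of 1.15 to 1.02 could be too high. The crude incidence uses one assumed hazard, and the gap narrows for very common events and is small in absolute terms for very rare ones. This stands.
- **The analysis is descriptive and single-arm, with no tests.** True, but the descriptive AE tables are the safety result, so an ambiguity in their counts matters.
- **The partial-date rule resolves itself** once the window is fixed. Largely so, though naming the study there costs only a few words.

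**Conclusion.** The concern holds. Sections 6.0 and 10.2 give incompatible starts for the same term, and no text reconciles them. The treatment-emergent AE counts and percentages depend on which section is followed. This must be corrected before the tables are produced.

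The difference in event counts is a factor of 1.84 at 52 weeks between first and last M06-807 injection, falling to 1.12 at 408 weeks. That range assumes a constant event rate, a 364-day parent period and equal follow-up across subjects. The contradiction itself rests on none of these assumptions.

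The undefined patient-years is a secondary point. It does harm only if person-time is taken over an interval that differs from the event window.

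**What to change.** 1. State one treatment-emergent window, in the same terms, in Sections 6.0 and 10.2. A start at the first M06-807 injection fits the SAP's safety population, Rx days and exposure definitions. A start at the first M06-806 dose is also workable if it is chosen openly and the person-time follows it.
2. Align the dose de-escalation paragraph of Section 10.2 with that window.
3. In the partial AE date rule of Section 6.0, name the study whose first dose is meant.
4. Define patient-years of observation for the safety population over the same start and end as the events, including the 70-day tail or to last contact if earlier. Apply it to all AE rates, including the dose de-escalation set and Section 10.5. Say explicitly that Section 9.0 exposure is not this denominator.
5. If the M06-807 start is chosen and all-adalimumab results from M06-806 onward are also wanted, give them in a separately labelled table with matching numerator and denominator. Note there that subjects had to complete M06-806 through Week 52. Deaths and discontinuations could therefore not occur in that year, although AEs leading to them later could have begun then.

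The cost is rewording in Sections 6.0, 10.2 and 10.5, a clarifying sentence on the Section 9.0 formula and, optionally, one extra AE table. No new data are needed.
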